### **DESCRIPTION OF PROTOCOL AMENDMENT**

Original Protocol Version 1.1. 20MAY2016 Amendment Version 1.2 Dated 16JUL2017

Amendment 1.3 Dated 28OCT2017

Number of global amendment		1.1
Date of CTP revision		20MAY2016
Protocol Number		FeCitrate
Title of protocol		Transition to Ferric Citrate among Hemodialysis and Peritoneal Dialysis Patients: A Phase 4 "Real World" Experience Study from Kaiser Permanente Southern California)
To be implemented only after approval of the IRB	X	
Section to be changed		Principal Investigator
Description of Change		[name] added
Section to be changed		Title Page
Description of Change		Amendment/Revision Section added 1.2.
Section To be changed		Table of Contents
Description of change		Table of Contents added protocol amendment summary to page 5 and updated table of contents pages
Section to be changed		Section 3: Study Design
Description of change		Added the following sentence to bullet point 3: "If study staff is unable to meet with patient during routine visit or if the patient requests more time to consider participation, peritoneal dialysis patients may be asked to return to clinic for an additional visit to sign the informed consent. This will only apply to peritoneal dialysis patients."
Section to be changed		Section 9.4 Study Calendar

Protocol Version 1.4, dated 26-Jun-2018

Description of change Footnote 4 added "If study staff is unable to r	
	with patient during routine visit or if the patient
	requests more time to consider participation,
	peritoneal dialysis patients may be asked to return to
	clinic for an additional visit to sign the informed
	consent. This will only apply to peritoneal dialysis
	patients."

### **DESCRIPTION OF PROTOCOL AMENDMENT**

Number of global amendment	1.2
Date of CTP revision	16JUL2017
Protocol Number	FeCitrate
Title of protocol	Transition to Ferric Citrate among Hemodialysis and Peritoneal Dialysis Patients: A Phase 4 "Real World" Experience Study from Kaiser Permanente Southern California)
Section to be changed	Title Page
Description of Change	Amendment/Revision Section changed to 1.3
Section To be changed	Table of Contents
Description of change	Updated table of contents pages
Section to be changed	Section 4.7 Concomitant Medication/Treatments
Description of Change	Removed "and cinacalcet (Sensipar)"
Section to be changed	Section 5.1.1. removed "3 to 19 pills per day"
Description of Change	Revised "3 to 19 pills per day" to 3+ pills"
Section to be changed	Throughout the protocol
Description of Change	Minor grammatical, formatting, or spelling change were made.

### DESCRIPTION OF PROTOCOL AMENDMENT

Number of global amendment	1.3
Date of CTP revision	280CT2017
Protocol Number	FeCitrate
Title of protocol	Transition to Ferric Citrate among Hemodialysis and Peritoneal Dialysis Patients: A Phase 4 "Real World" Experience Study from Kaiser Permanente Southern California)
Section to be changed	Title Page
Description of Change	Amendment/Revision Section changed to 1.4
Section To be changed	Table of Contents
Description of change	Updated table of contents pages
Section to be changed	Description of Protocol Amendment version 1.1
Description of Change	Number of global amendment and date of CTP Version
Section to be changed	List of Abbreviations
Description of Change	Minor format change
Section to be changed	Section 3.0 Study Design
Description of Change	Added the following sentence to bullet point #3. "If at any time during the study, a peritoneal, dialysis patient changes to hemodialysis, the patient can continue study at the principal investigator's discretion. If at any time during the study, a hemodialysis patient changes dialysis to peritoneal, the patient can continue on study at the principal investigator's discretion. In such event, patient's group assignment for analysis will be determined at the discretion of the Principal Investigator. Patients will be allowed to continue in the trial given that they can continue to meet all study participation requirements."
Section to be changed	Section 7.2 Criteria for Removal from Treatment

Protocol Version 1.4, dated 26-Jun-2018

Proprietary Information. Kaiser Permanente. All rights reserved. Template v2.0

Description of Change	Added the following: "7.2.6 At the discretion of the principal investigator, a patient may be removed from the study if they initiate dialysis care at a non- outside/Non-Kaiser Permanente facility."
Section to be changed	Throughout the protocol
Description of Change	Minor grammatical, formatting, or spelling change were made.

### LIST OF ABBREVIATIONS

AE	Adverse Event/Adverse Experience
CFR	Code of Federal Regulations
ESA	Erythropoiesis Stimulating Agent
CRO	Contract Research Organization
ESRD	End Stage Renal Disease
FDA	Food and Drug Administration
FWA	Federalwide Assurance
GCP	Good Clinical Practice
HIPAA	Health Insurance Portability and Accountability Act
ICF	Informed Consent Form
ICH	International Conference on Harmonisation
IDE	Investigational Device Exemption
IND	Investigational New Drug Application
IRB	Institutional Review Board
PHI	Protected Health Information
PI	Principal Investigator
SAE	Serious Adverse Event/Serious Adverse Experience

### **PROTOCOL SUMMARY**

Title	Transition to Ferric Citrate among Hemodialysis and Peritoneal Dialysis Patients: A Phase 4 "Real World" Experience Study from Kaiser Permanente Southern California		
Short Title	FeCitrate		
Protocol Number	KP FeCitrate		
Study Phase	4		
Study Site(s)	Los Angeles Kaiser Sunset Medical Center		
Number of Subjects	55		
Study Arms	1		
Indication	Hyperphosphatemia in end stage renal disease		
Primary Purpose	To evaluate the efficacy of ferric citrate for control of serum phosphorus levels and maintenance of adequate iron stores among dialysis-dependent patients before and after conversion from traditional phosphate binders in a "real world" environment		
Overview of Study Design	prospective non-randomized cohort study of 6-9 months duration (active study period 6 months).		
Investigational Product Administration	One to two tablets of Ferric Citrate phosphorus binder administered by mouth before every meal to prevent dietary phosphorus absorption.		
Eligibility Criteria	
 
Inclusion criteria:
 
On 3 + per day of calcium acetate, sevelamer, lanthanum, aluminum, or calcium carbonate
 
Mean serum phosphorus 4.0-<8.0 mg/dl for the past 6 months
 
No allergy to iron
 
Mean corrected calcium >8.0mg/dl for past 6 months
 
		
	
 
Mean PTH < 1000 pg/ml for past 6 months
 
		

	• Mean ferritin < 1500 ng/ml and mean iron sat < 50% for past 6	
	months	
	Patients with diabetes will be included	
	Exclusion criteria	
	History of gastrointestinal bleeding within past 6 months	
	History of hospitalization for gastroparesis, bowel obstruction,	
	or abdominal surgery within past 6 months	
	Active malignancy	
	Renal transplant	
	History of autoimmune disease, hemoglobinopathy,	
	hemochromatosis, or sickle cell disease	
Study Endpoint	Mean serum phosphorus levels and rate of successful phosphorus control (<5.5mg/dl) 6 months before and after treatment with ferric citrate	
Statistical Methods	Not powered to detect statistical significance	

### **1 INTRODUCTION**

### 1.1 Background

High serum phosphorus levels are associated with a greater risk of mortality among patients with chronic kidney disease (CKD) and non-chronic kidney disease populations(1-5). Elevated phosphorus levels are also associated with increased cardiovascular complications among dialysis patients. As renal function declines, dietary intake and adherence to phosphate binders becomes more and more important for phosphorus control and prevention of CKD-associated mineral bone disease (CKD-MB).

Reduction of serum phosphorus levels by phosphate binding agents is associated with a lower risk of both cardiovascular and all-cause mortality in patients with end stage renal disease (ESRD)(6), but side effects of phosphate binders, high pill burden, and long term safety concerns remain an issue. Calcium based binders are associated with vascular calcifications(7, 8), which led to national guidelines that limit total elemental calcium intake in ESRD patients. Aluminum hydroxide and lanthanum carbonate are potential alternatives to calcium based binders and sevelamer carbonate/hydrochloride, but pose the risk for long term buildup in the body and potential untoward consequences since they are metals. (9, 10)

While much effort is placed on dietary counseling regarding low phosphorus diets, proper use of phosphate binders and vitamin D analogs, a high prevalence of CKD-MB associated complications still exists among patients, especially dialysis dependent patients. Valvular heart disease, isolated systolic hypertension, calcific uremic ateriolopathy (calciphylaxis), peripheral vascular disease, and hip fractures are all more common in CKD patients, leading to greater morbidity and mortality(11, 12). The pathophysiology of vascular disease in CKD patients is complex. It occurs as a consequence of reduced renal function, increases in calcium and phosphorus balance, precipitation of calcium and phosphorus and the uremic milieu. Previous observations using electron beam computed tomography have demonstrated an association between higher calcification and cardiovascular disease.(12, 13)

Circulatory function is further compromised by declining hemoglobin levels and anemia in the CKD population. The insufficient erythropoiesis that occurs as renal function declines likely compounds the vascular pathology that occurs in the setting of CKD-MB. In addition, elevated serum phosphorus levels and associated hyperparathyroidism lead to bone marrow suppression, compounding the anemia. Erythropoiesis stimulating agents (ESA's) are a routine part of management of patients with CKD/ESRD, but are not without adverse effects, including an increased risk of cardiovascular events, mortality, and malignancy. Current recommendations regarding use of ESA's in ESRD patients are to use the minimum dose required to prevent blood transfusion. Maintenance of adequate iron stores ensures adequate erythropoiesis and avoids excessive use of ESA's.

Control of serum phosphorus levels can be a challenge for patients with ESRD and depends largely on patient adherence to diet and phosphate binder use. Many patients have difficulty tolerating binders, possibly due to pill size and high pill burden(14, 15). It is not unusual for ESRD patients to consume upwards of 10 pills per day in an effort to control serum phosphorus levels. Simpler medication regimens for phosphorus control would likely result in improved compliance and better outcomes for patients with ESRD.

1.2 Study Medication

Ferric citrate is an iron-based phosphate binder approved by the FDA for control of serum phosphorus levels in patients with chronic kidney disease on dialysis. It has been shown to increase serum iron parameters, including ferritin, iron and TSAT. In dialysis patients treated with ferric citrate in a 52-week study in which IV iron could also be administered, mean (SD) ferritin levels rose from 593 (293) ng/mL to 895 (482) ng/mL, mean (SD) TSAT levels rose from 31% (11) to 39% (17) and mean (SD) iron levels rose from 73 (29) mcg/dL to 88 (42) mcg/dL. In contrast, in patients treated with active control, these parameters remained relatively constant.

1.3 Preclinical Data

Ferric citrate has already been FDA approved.

1.4 Clinical Data to Date

Ferric citrate coordination complex (ferric citrate) is an intestinal phosphate binder that has been shown previously to replete iron stores, increase hemoglobin levels, and reduce serum phosphate levels in patients with ESRD undergoing hemodialysis.

1.5 Hypothesis

We seek to determine the efficacy and potential pleotropic effects of the new FDA approved phosphorus binder, ferric citrate, in patients with ESRD, including both hemodialysis and peritoneal dialysis patients. This study is expected to expand upon results obtained in previous published studies, providing "real world" experience with ferric citrate.

### **2 OBJECTIVES AND PURPOSE**

### SPECIFIC AIMS

 To determine efficacy and tolerability of ferric citrate in dialysis-dependent patients treated for hyperphosphatemia

Protocol Version 1.4, dated 26-Jun-2018

Page 13 of 35

- 2) To compare dose efficacy of ferric citrate to calcium acetate and sevelamer carbonate for control of serum phosphorus levels
- To determine changes in iron saturation and ferritin after conversion to ferric citrate
- 4) To determine iron requirements after conversion to ferric citrate
- 5) To determine changes in hemoglobin after conversion to ferric citrate
- 6) To determine ESA doses and requirements after conversion to ferric citrate

### **3 STUDY DESIGN**

- Type: non-randomized, single arm, phase IV, cohort pilot study
- Study population: end stage renal disease patients who are on chronic hemodialysis or peritoneal dialysis with elevated serum phosphorus.
- 55 chronic dialysis patients (28 hemodialysis and 27 peritoneal dialysis) who are currently using oral phosphorus binders will be enrolled. Potential participants will be screened from both the chronic hemodialysis unit and the home dialysis unit at the LAMC site. Potential study patients will be approached by study investigators during any routine visit. If the patient consents to participation, the study coordinator will see patients during the same visit. If study staff is unable to meet with patient during routine visit or if the patient requests more time to consider participation, peritoneal dialysis patients may be asked to return to clinic for an additional visit to sign the informed consent. This will only apply to peritoneal dialysis patients. If the patient chooses not to enter the study, the reason will be noted by the study coordinator. At the appropriate time in the study, the study coordinator will dispense the study medication, Ferric Citrate, and provide instructions per study protocol. The study coordinator will meet with the participant every month during either a hemodialysis visit (for hemodialysis patients) or a monthly clinic visit (for peritoneal dialysis patients) with his/her provider, and laboratory values/data and study questionnaire will be updated each month. If at any time during the study, a peritoneal, dialysis patient changes to hemodialysis, the patient can continue study at the principal investigator's discretion. If at any time during the study, a hemodialysis patient changes dialysis to peritoneal, the patient can continue on study at the principal investigator's discretion. In such event, patient's group assignment for analysis will be determined at the discretion of the Principal Investigator. Patients will be allowed to continue in the trial given that they can continue to meet all study participation requirements. The six month period prior to enrollment will be used to evaluate the

participants' baseline laboratory values and medication use, including phosphorus binder use. Laboratory values and medication use will also be evaluated and recorded monthly during the six months of active study. The duration of the study will be six months on ferric citrate. At the end of the study, the participant can be provided with a prescription of ferric citrate by his/her nephrologist if the participant wishes to continue with ferric citrate, or he/she can go back to the phosphorus binder used before enrolling in this study.

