#### 3.1 Treatment Arms

This is a single arm study in which all participants will be changed to the study medication for a total of six months.

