### **6** STRATIFICATION/ RANDOMIZATION SCHEME

No stratification or randomization scheme is needed in this single arm study.

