## 9.1.4 Lab draw 2 weeks and 6 weeks into the study (L0.5, L1.5) with optional visit ± 7 days

Participant will have lab draw 2 weeks into the study, and possibly again 6 weeks into the study (if deemed necessary by the study investigator), in between their routine monthly labs, to help adjust the study drug dose to control the serum phosphorus level.

- Collect blood specimens at dialysis unit for complete blood count, iron saturation, ferritin, phosphorus, calcium
- Study coordinator will review laboratory tests with study investigator to assess if study drug dose adjustment is needed.
- Optional visit by study coordinator with the patient to review study medication dosage change

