### **10 CRITERIA FOR EVALUATION AND ENDPOINT DEFINITIONS**

### 10.1 Primary Endpoints

Mean serum phosphorus levels and rate of control (<5.5mg/dl) 6 months before and after treatment with ferric citrate, including PTH, calcium, iron saturation, ferritin, hemoglobin and aluminum levels

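### The HD or PD analysis group of a patient who switches modality is left to the Principal Investigator, with nothing to stop the choice following the outcome

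*Combined protocol and SAP*

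**What the plan says.** Section 3 fixes enrolment by modality: "55 chronic dialysis patients (28 hemodialysis and 27 peritoneal dialysis) who are currently using oral phosphorus binders will be enrolled". It then covers a change of modality during the study: "If at any time during the study, a peritoneal, dialysis patient changes to hemodialysis, the patient can continue study at the principal investigator's discretion". A parallel sentence covers HD to PD. The rule for analysis follows: "In such event, patient's group assignment for analysis will be determined at the discretion of the Principal Investigator".

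No other section narrows that rule. Section 6 says "No stratification or randomization scheme is needed in this single arm study", and Section 14.4 (Final Analysis Plan) is N/A.

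The primary endpoint in Section 10.1 is "Mean serum phosphorus levels and rate of control (<5.5mg/dl) 6 months before and after treatment with ferric citrate". It is not split by modality, and neither are the aims in Section 2 or the secondary endpoints in Section 10.2.

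**The concern.** A patient's analysis group should be fixed by something known before the outcome. Here it is fixed by a judgement made after a switch, and the switch may come at any point in the six months on drug. Section 3 says of the monthly contacts that "laboratory values/data and study questionnaire will be updated each month", and everyone receives open-label ferric citrate, so phosphorus values may already be on file when the judgement is made. The protocol does not say the choice will use outcomes, but nothing prevents it.

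What is at stake is any result shown separately for HD and PD. No such result is formally specified. However, the 28/27 enrolment split, the interest in both modalities stated in Section 1.5, and the reference to an analysis group all point to one; in a single-arm study, a group tied to a change of modality can only mean HD or PD. A reader of that breakdown could not rule out that switchers were placed with their results in view.

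**Working it through.** **Text check.** The protocol was searched for anything that would fix a switcher's group.

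| Question | Where it would be | What is there |
|---|---|---|
| Default group | Section 3 | None; investigator's discretion |
| Criterion or deadline | Section 3 | None |
| Stratum fixed at entry | Section 6 | No stratification |
| Rule in the analysis plan | Section 14.4 | N/A |
| Masking | Section 3.1 | Single arm, all on study drug |
| Outcomes visible during the study | Section 3 | Laboratory values recorded monthly |

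The lab-draw section (9.1.4, weeks 2 and 6) adds "Study coordinator will review laboratory tests with study investigator to assess if study drug dose adjustment is needed". That shows study investigators see interim values, though it concerns dosing and does not name the Principal Investigator. The monthly recording in Section 3 is the stronger basis.

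**Figures in the plan.** There is no sample-size or power figure to reproduce: Section 14.2 is N/A and the Protocol Summary says the study is not powered. The one arithmetic check is 28 + 27 = 55, which agrees.

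**Size of the effect.** Inputs from the protocol: 28 HD and 27 PD. Assumptions, because the protocol gives no values:
- the same control rate p in both groups, from 0.4 to 0.7;
- k = 1, 2 or 3 PD-to-HD switchers;
- any number of those switchers controlled;
- one controlled/uncontrolled status per patient.

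If *a* controlled and *b* uncontrolled switchers are labelled HD, the HD–PD difference is

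(28p + a)/(28 + a + b) − (27p − a)/(27 − a − b).

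The span is the largest minus the smallest value over all labellings open to the investigator. The table gives it in percentage points; each range runs over the mix of controlled and uncontrolled switchers.

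| p | k = 1 | k = 2 | k = 3 |
|---|---|---|---|
| 0.4 | 2.9–4.4 | 5.9–8.8 | 8.9–13.3 |
| 0.5 | 3.6 | 7.3 | 11.0–11.1 |
| 0.6 | 2.9–4.4 | 5.9–8.8 | 8.9–13.3 |
| 0.7 | 2.2–5.1 | 4.4–10.3 | 6.7–15.5 |

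Worked cell: p = 0.7, k = 3, all uncontrolled.
- All three left in PD: 19.6/28 − 18.9/27 = 0.
- All three labelled HD: 19.6/31 − 18.9/24 = 0.632 − 0.788 = −0.155 after rounding, a span of 15.5 points.
- The same case with HD-to-PD switchers: 19.6/25 − 18.9/30 = 0.154. Across the table the two directions agree within 0.2 point.

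The standard error of the difference is √[p(1 − p)(1/28 + 1/27)]: 13.2, 13.5, 13.2 and 12.4 points for p = 0.4, 0.5, 0.6 and 0.7. One switcher is therefore worth about 0.2–0.4 standard errors, and three about 0.5–1.3.

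**Illustration with whole patients.** Assume 14/28 HD and 14/27 PD controlled. By modality at enrolment, PD minus HD is 51.9% − 50.0% = +1.9 points. Now relabel three PD patients as HD.
- If all three are uncontrolled: 14/24 − 14/31 = +13.2 points.
- If all three are controlled: 11/24 − 17/31 = −9.0 points.

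The pooled rate is 28/55 = 50.9% throughout.

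**The case against.** The strongest objection is that no planned result depends on the label. Aims, endpoints and hypothesis contain no HD/PD comparison, and this is an unpowered feasibility pilot. Harm requires both that a by-modality table is produced and that someone switches. This stands as a limit on importance. It does not remove the point, because the protocol chose to write a rule for analysis groups and that rule permits assignment after the outcome is known.

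The spans above are bounds under the worst use of the discretion, not expected bias. The largest needs three switchers, all uncontrolled, at p = 0.7. The model also uses one yes/no status per patient, whereas Section 10.1 refers to control over six months and to mean phosphorus, for which no effect was calculated. All of this is fair.

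The statement that pooled results do not change is true of the group label only. The same paragraph leaves a switcher's continuation to the investigator's discretion, and no analysis population is defined. In the whole-patient illustration, leaving out three discontinued switchers would move the pooled rate from 50.9% to 28/52 = 53.8% (all uncontrolled) or 25/52 = 48.1% (all controlled). That is a separate matter, which the fix below does not address.

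**Conclusion.** The concern holds, within a narrow scope. The current text assigns switchers to an analysis group by unconstrained discretion, in an unmasked study whose outcomes accumulate monthly. Any HD/PD breakdown that includes switchers is exposed; the label has no effect on the pooled before/after endpoints.

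Under the assumed control rates, the exposure in the HD–PD difference is 2.2–5.1 points with one switcher, 4.4–10.3 with two and 6.7–15.5 with three. It is nil with none. A single switcher matters little beside the sampling error; three could shift the difference by up to about 1.3 standard errors. The change should be made because it is cheap and the present rule cannot be defended to a reader, not because the main result is at risk.

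**What to change.** Replace the sentence on group assignment in Section 3 with wording such as: *Patients are analysed in the modality group recorded at enrolment; the number of switchers is reported, and a sensitivity analysis censors data at the date of the switch.* Modality at first dose would serve equally well, since it too is fixed before any on-drug outcome. The discretion over continued participation need not change for this purpose.

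The cost is one sentence, one additional descriptive table and the date of each switch, with no extra patients or visits. There are two small drawbacks. An early switcher is counted mostly under a modality no longer in use, which the sensitivity analysis addresses. In that analysis the same patient contributes few on-drug months against a full six-month baseline, so the table should show the on-drug time that switchers contribute.
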